7.1.1. Intensity Assessment

The investigator or the designated person will provide an assessment of the severity of each AE by recording a severity rating on the appropriate AE reporting page of the subject's electronic case report form (eCRF). In classification of AEs, the term "severe" is not the same as "serious". Severity is a description of the intensity of a specific event (as in mild, moderate, or severe chest pain). The term "serious" relates to a participant/event outcome or action criteria, usually associated with events that pose an immediate threat to a participant's life or functioning, and meets one or more of the SAE criteria described above.

The Division of AIDS (DAIDS) Table for Grading the Severity of Adult and Pediatric Adverse Events, Version 2.1 will be used for assessing AEs ([DAIDS Table for Grading the Severity of Adult and Pediatric Adverse Events, Version 2.1. \[July 2017\]](#)). All AEs will be graded as grade 1 (mild), grade 2 (moderate), grade 3 (severe), grade 4 (potentially life-threatening) or grade 5 (death) according to the definitions described in the DAIDS Table. Every effort will be made to obtain an adequate evaluation of the severity.

7.1.2. Causality Assessment

The qualified investigator or a medically qualified designate will determine the relationship of any AE to study drugs using the following guidelines in Table 6-2.

Table 6-2 Adverse Event Relationship to Study Drug

Relationship to Drug	Comment
Reasonable Possibility	There is evidence to suggest a causal relationship between the drug(s) and the AE (e.g., AE is uncommon and known to be strongly associated with drug exposure or is uncommon in the study population, but not commonly associated with drug exposure).
No Reasonable Possibility	There is no evidence to suggest a causal relationship between the drug(s) and the AE.

7.2. Routine Reporting

For the purposes of this study, non-serious AEs and SAEs will be recorded in the eCRF from the time of informed consent until the end of the study.

During these periods, all AEs spontaneously reported by the subject, observed by the clinical staff, or elicited by general questioning will be recorded and reported in the eCRF.

Protocol Number: AT-03A-001

Any AE which remains unresolved as of the last visit will require follow-up until the AE has been resolved, a reasonable explanation for its persistence found, or is deemed chronic or stable but the investigator. It is the investigator's responsibility to ensure subjects experiencing AEs receive appropriate follow-up, treatment where required, and that every action is well documented.

Classification will be performed by System Organ Class (SOC) and preferred term using the Medical Dictionary for Regulatory Activities (MedDRA).

In general, AEs occurring secondary to other events (e.g., clinical sequelae or a cascade of events) should be identified by their primary cause. For example, if severe vomiting is known to result in dehydration, it is sufficient to record only vomiting as an SAE or AE in the eCRF. However, medically significant AEs occurring secondary to an initiating event that are separated in time should be recorded as independent events on the eCRF.

7.3. Serious Adverse Event Reporting

Clinical sites must notify [REDACTED] of any SAE, without regard to causality, within 24 hours after becoming aware of its occurrence. Any non-serious AE which worsens and eventually meets the criteria for an SAE must also be reported as a new SAE.

Information regarding SAEs will be transmitted to [REDACTED] using the Serious Adverse Event form in the electronic data collection tool, which must be completed by a member of the investigational site staff within 24 hours. This form should include a clearly written narrative describing diagnostic terms, signs, symptoms and treatment of the event, diagnostic procedures, as well as any relevant laboratory data and an assessment of the potential causal relationship between the event and the investigational product(s). Information not available at the time of the initial report (e.g., an end date for the AE, laboratory values received after the report, or hospital discharge summary) must be documented. All follow-up information must be reported as soon as the relevant information is available.

If the electronic system is unavailable, then the site will use the paper SAE data collection tool and transmit to [REDACTED] within 24 hours by one of the following methods:

Email: [REDACTED]

Fax: [REDACTED]

The site will enter the SAE data into the electronic system as soon as it becomes available.

Contact information for the Sponsor's physician is also listed below, should the sites need to contact the Sponsor to discuss any medical, safety related questions or SAEs:

[REDACTED]
[REDACTED]
[REDACTED]

An unlisted (unexpected) AE is one in which the nature or severity is not consistent with the applicable product reference safety information. For investigational product(s), the expectedness of an AE will be determined by whether or not it is listed in the Investigator's Brochure(s). At this time in the clinical development of AT-527, based on non-clinical data and limited clinical experience to date, there are no clinical AEs or clinically significant laboratory abnormalities that

Protocol Number: AT-03A-001

are considered to be “expected” with AT-527, at any dose level. Investigators will be notified, and the Investigator Brochure will be updated, if any pattern of AEs or laboratory abnormalities is found to be related to AT-527 dosing during studies going forward.

The start date of an SAE reported on the Serious Adverse Event form must be the same as the start date of the corresponding AE documented on the eCRF. If a change in severity is noted for the existing AE, it must be recorded. If a worsened AE meets the criteria for an SAE, the start date of the SAE must be the same as the start date of the worsened AE.

All SAEs that have not resolved by the end of the study, or that have not resolved upon discontinuation of the subject’s participation in the study, must be followed until any of the following occurs:

- the event resolves;
- the event stabilizes;
- the event returns to baseline, if a baseline value is available;
- the event can be attributed to agents other than the study drugs or to factors unrelated to study conduct;
- it becomes unlikely that any additional information can be obtained (subject or health care practitioner refusal to provide additional information, lost to follow-up after demonstration of due diligence with follow-up efforts).

Any SAE reports will be reported by the investigators (or designee) to their local IRB/IEC in accordance with local reporting requirements and reporting timelines.

Similarly, the Sponsor (or designee) will determine whether an SAE must be reported in an expedited manner to regulatory authorities, in accordance with regulatory requirements. If so, the Sponsor (or designee) will report the event to the regulatory authorities in accord with applicable reporting timelines.

7.4. Pregnancy Reporting

All initial reports of pregnancy must be reported to [REDACTED] (see [Section 7.3](#) for contact information) by the investigational staff within 24 h of their knowledge of the event using the paper Pregnancy Reporting Form provided. After the expected delivery date and/or once an outcome is known, the site will provide [REDACTED] with pregnancy outcome, delivery, and infant details for completion of reporting. Abnormal pregnancy outcomes are considered SAEs and must be reported using the electronic Serious Adverse Event Form. Any subject who becomes pregnant during treatment must immediately discontinue study drugs.

In addition, pregnancies in partners of male subjects included in the study will be reported by the investigational staff within 24 h of their knowledge of the event using the paper Pregnancy Reporting Form.

8. STATISTICAL ANALYSES

This section summarizes the statistical analyses pertinent to the efficacy and safety assessments in this study. A statistical analysis plan (SAP) describing the detailed statistical methods for this study will be prepared and finalized before database lock. Sample size calculations and power

Protocol Number: AT-03A-001

statements, with the exception of those for time to Clinical Recovery, were performed using SAS/STAT v9.4 (SAS Institute Inc., Cary, NC, USA). The power estimates for time to Clinical Recovery were computed by simulation. Corresponding code is provided in [Section 13](#).

All analyses of trial data will be performed in this version of SAS/STAT or higher unless noted in the eventual SAP that other software will be utilized.

This is a double-blind randomized study, with variable size block randomization stratified by region.

In order to support interactions with regulatory agencies, the Sponsor may choose to conduct interim analyses during the course of the study. The decision to conduct an interim analysis and the timing of the analysis will be documented in the Sponsor's trial master file prior to the conduct of the interim analysis. The interim analysis will be performed and interpreted by members of the Sponsor study team and appropriate senior management personnel, who will be unblinded at the treatment group level.

8.1. Analysis Populations

8.1.1. Safety Population

The safety population will include all subjects who received at least one dose of the study drug (AT-527 or placebo). The study population will be analyzed as treated.

8.1.2. Intention To Treat Population

The intention to treat (ITT) population will include all randomized subjects and will be analyzed as randomized.

8.1.3. Modified Intent-to-Treat Population

The Modified Intent-to-Treat (mITT) analysis set will contain subjects in the ITT analysis set with positive qualitative SARS-CoV-2 RT-PCR test result at baseline from the central laboratory and who receive at least one dose of study drug (AT-527 or placebo).

For analyses and displays based on mITT analysis set, subjects will be classified according to randomized treatment.

8.1.4. Per Protocol Population

The per protocol (PP) population will include the subset of the ITT subjects who completed the study drug regimen without major protocol violations that would potentially affect the study's primary endpoints.

8.1.5. PK Populations

The PK population will include all subjects who received at least one dose of AT-527 and for whom evaluable plasma concentration data are available. Subjects who received placebo will not be included in the PK population.

Protocol Number: AT-03A-001

8.2. Endpoints

8.2.1. Primary Efficacy Endpoint and Sample Size Calculations

Part A

The primary endpoint for Part A of this study is the proportion of subjects with PRI, defined as a ≥ 2 -tier increase in respiratory support methods required to maintain satisfactory oxygenation ($\text{SpO}_2 \geq 93\%$), using the 6-tier hierarchical scale of Respiratory Support methods described in **Section 6.9**.

The primary efficacy goal is to reduce the incidence of PRI by 50% for active-dosed subjects compared to placebo recipients. The featured timeframe for this primary endpoint analysis will be the 14-day primary study period, with secondary analyses at study Days 10, 21, and 28.

With this study's relatively high-risk COVID-19 subject population (one or more known risk factors for poor outcomes), the study postulate is that 40% of placebo recipients will experience PRI during the 14-day study period, and the efficacy goal is therefore to reduce that incidence of PRI to 20% or less in active recipients.

Assuming PRI rates (PRIR) of 0.4 and 0.2 in the control and experimental arms, respectively, at alpha one-sided of 0.025, and at a power of 0.8, a total of 182 subjects are required at a 1:1 allocation, i.e. 91 per study arm. The study statistical hypotheses are as follows:

$$H_0: \text{Experimental}_{\text{PRIR}} \geq \text{Control}_{\text{PRIR}}$$

$$H_a: \text{Experimental}_{\text{PRIR}} < \text{Control}_{\text{PRIR}}$$

Part B

The primary endpoint of Part B is the change from baseline in amount of SARS-CoV-2 virus RNA (viral load) as measured by RT-PCR. Viral load will be assessed quantitatively using a validated assay. Analyses will be carried out at each scheduled time point using the mITT population. Part B of the study is signal seeking. The primary analysis aims to identify and characterize any potential effect of AT-527 on viral load over time. Analyses and p-values are descriptive and no adjustment for multiple comparisons will be made.

Change from baseline viral load at a timepoint will be compared between the AT-527 group and the placebo group ANCOVA with treatment as a factor and \log_{10} baseline viral load as a covariate. In the interim analysis of the first 70 subjects from part A, the observed AT-527 effect at Day 2 was a reduction of 0.7 \log_{10} copies/mL relative to placebo. Assuming a standard deviation for change from baseline of 1.8 \log_{10} copies/mL and 90% of Part B randomized patients eligible for analysis (i.e. 100 patients), there is at least 90% power to detect a true treatment effect of 0.7 at a timepoint using a one-sided test at 0.1 level of significance, not adjusted for multiple comparisons.

Protocol Number: AT-03A-001

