	
Part B
 
The primary endpoint of Part B is the change from baseline in amount of SARS-CoV-2 virus RNA (viral load) as measured by RT-PCR. Viral load will be assessed quantitatively using a validated assay. Analyses will be carried out at each scheduled time point. Part B of the study is signal seeking. The primary analysis aims to identify and characterize any potential effect of AT-527 on viral load over time. Analyses and p-values are descriptive and no adjustment for multiple comparisons will be made.
 
Change from baseline viral load at each timepoint will be compared between the AT-527 group and the placebo group ANCOVA with treatment as a factor and log₁₀ baseline viral load as a covariate. In the interim analysis of the first 70 subjects from part A, the observed AT-527 effect at Day 2 was a reduction of 0.7 log₁₀ copies/mL relative to placebo. Assuming a standard deviation for change from baseline of 1.8 log₁₀ copies/mL and 90% of Part B planned randomized patients eligible for analysis (i.e. 100 patients), there is at least 90% power to detect a true treatment effect of 0.7 using a one-sided test at 0.1 level of significance.
 
Only patients with a positive qualitative SARS-CoV-2 RT-PCR test result at baseline will be included in this analysis. The least squares mean (LSM) change and its standard error of means (SE) in each group, the differences between two groups in LSM change with corresponding 95% confidence intervals (CIs), and p-values will be presented.
 
Key secondary endpoints:
 
The efficacy endpoint assessments are hierarchical in Part A. The key secondary endpoints will be tested, in order, only if the primary efficacy endpoint meets its success criteria and each higher endpoint meets its success criteria. This hierarchical testing strategy will preserve study alpha.
 
The key secondary endpoints for Part A are indicated below with the hierarchical ordering. The hierarchical ordering pertains to Part A only. Following the change in protocol following the interim analysis, there will be no formal procedure to preserve study-wise type I error in Part B. All analyses are descriptive, and any findings would need to be confirmed in another study with prospective alpha control. With the change in primary endpoint in Part B, the primary endpoint and non-virological key secondary endpoints from Part A will be considered as key secondary endpoints in Part B.
 
• First key secondary endpoint (Part A only): change from baseline in amount of SARS-CoV-2 virus RNA (viral load) as measured by RT-PCR. 
Viral load will be assessed quantitatively using a validated assay. Change from baseline viral load will be compared between the AT-527 group and the placebo group at scheduled time points using ANCOVA with treatment as a factor and log₁₀ baseline viral load as a covariate. The least squares mean (LSM) change and its standard error of means (SE) in each group, the differences between two groups in LSM change with corresponding 95% confidence intervals (CIs), and p-values will be presented. Statistical significance at Day 5 will be assessed using a one-sided 0.025 level test. If the Day 5 comparison is significant, then the Day 2 treatment effect would be tested.
 
• Second key secondary endpoint: median time (days) to Clinical Recovery from randomization, based on achieving disease resolution (status 6, 7, or 8) in the NIAID Clinical Status scale

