disease progression to successive stages of respiratory insufficiency is potentially lifesaving, as ultimate progression to dependence on intubated respiratory support is associated with a high rate of fatal outcomes (over 50% in U.S. patients, and over 80% in ex-U.S. patients, as noted above).

Additional information for AT-527 can be found in the [AT-527 Investigator's Brochure](#).

Rationale/Background for Amendment 8

[figure not shown]
The clinical development program has been designed on the basis of the emergency nature of the ongoing pandemic. Although the initial primary efficacy goal of the originally designed study was to significantly reduce progressive respiratory insufficiency (PRI), it has become apparent, from blinded analysis, that the background rates of disease progression in this targeted study population are too low to demonstrate clinical efficacy differences between the treatment arms. With a better understanding of the disease resulting in improvements in patient management over time, the disease progression rates observed in this study are much less than the initial assumptions made at the beginning of the study/pandemic, which postulated that 40% of placebo recipients would progress and experience PRI. Due to the low progression rates and in order to support interactions with regulatory agencies, the Sponsor decided to pause enrolment and conduct an interim analysis during the course of the study.

Enrollment in the study was paused after the 81st patient was randomized and the interim analysis (in which the study team remained blinded to individual treatment assignment) was performed on the first 70 patients who completed through Day 14 of the study. Of 62 patients evaluable for the virology analysis, 58 had baseline quantitative viral load data. This interim analysis indicated that AT-527 rapidly reduced viral load levels. At Day 2, patients receiving AT-527 experienced a 0.7 log₁₀ greater mean reduction from baseline viral load as compared to placebo. A sustained difference in viral load reduction was maintained through Day 8 (see figure below). After Day 8, the curves in the groups converge, however, this is expected considering the natural history of the disease in which viral load generally peaks at the time of symptom onset and decreases spontaneously with time.

Protocol Number: AT-03A-001

Quantitative SARS-CoV-2 RNA, mITT (all evaluable patients)
Viral Load **Change from Baseline**

[figure not shown]

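### Part B's stated power of at least 90% is wrong: 100 evaluable patients in total give about 75% for a 0.7 log10 effect

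*Protocol*

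**What the plan says.** Protocol Section 8.2.1 (Part B) makes the primary endpoint the change from baseline in viral load, compared at each timepoint by ANCOVA with treatment as a factor and log10 baseline viral load as covariate. The power statement rests on four inputs:

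- Effect: in the first 70 Part A subjects "the observed AT-527 effect at Day 2 was a reduction of 0.7" log10 copies/mL relative to placebo.
- Variability: "Assuming a standard deviation for change from baseline of 1.8" log10 copies/mL.
- Evaluable patients: 90% of those randomized in Part B, given as 100 patients.
- Test: "using a one-sided test at 0.1 level of significance, not adjusted for multiple comparisons".

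The conclusion drawn is that "there is at least 90% power to detect a true treatment effect of 0.7 at a timepoint using a one-sided test at 0.1 level". The Part B paragraph of the synopsis (Statistical Methods) says the same: "there is at least 90% power to detect a true treatment effect of 0.7 using a one-sided test at 0.1 level of significance".

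Sections 3.1 and 3.2 set Part B at up to 110 additional subjects, and Section 3.1 gives 1:1 randomization. SAP Section 7.1 carries no Part B power calculation, so these two protocol statements are the only ones.

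**The concern.** Ninety percent of 110 is 99, so the 100 evaluable patients must be the total over both arms. About 50 per arm is small for a standardized difference of 0.7/1.8 = 0.39, even at a one-sided 0.1 level, and a claim of at least 90% looks too high.

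Part B is described as signal seeking, and Section 1.1 (rationale for Amendment 8) says its results would support dose selection. For such a study the probability of missing a real effect is the operating characteristic that matters most. A reader who believes it is at most 10% may take a flat Part B result as evidence against an antiviral effect at the higher dose, when the design would miss a true 0.7 log10 effect about one time in four.

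**Working it through.** **Inputs.** Difference 0.7; SD of change 1.8; one-sided alpha 0.1, critical value 1.2816 (all Section 8.2.1); 100 evaluable in total (Section 8.2.1; 0.9 × 110 = 99); 1:1 allocation (Section 3.1), so 50 per arm.

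**Formula.** SE = SD × √(2/n per arm); power = Φ(difference/SE − 1.2816).

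**Trying to reproduce the plan's figure.** With the stated inputs:

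- SE = 1.8 × √(2/50) = 0.36
- 0.7/0.36 = 1.944; 1.944 − 1.2816 = 0.663
- Power = Φ(0.663) = 74.6%

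The noncentral t gives 74.4%, whether on 98 degrees of freedom or on 97 to allow for the covariate. The stated figure is not reproduced. Variants, all with difference 0.7 and SD 1.8:

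| Variant | Power |
|---|---|
| 99 evaluable in total, one-sided 0.1 | 74.3% |
| All 110 evaluable (55 per arm), one-sided 0.1 | 77.6% |
| 50 per arm, two-sided 0.1 | 61.8% |
| 50 per arm, one-sided 0.2 | 86.5% |
| 100 **per arm**, one-sided 0.1 | 92.9% |

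For the last row, SE = 1.8 × √(2/100) = 0.2546; 0.7/0.2546 = 2.750; 2.750 − 1.2816 = 1.468; Φ(1.468) = 92.9%. Of the variants tried, this is the one that uses the number 100 and satisfies the claim at the stated alpha and SD. The likely explanation is that the total was entered as the per-arm size, but that is an inference.

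**What 90% power would need.**

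- Sample size: 2 × (1.8/0.7)² × (1.2816 + 1.2816)² = 86.9, so 87 per arm (88 by t). That is 174 to 176 evaluable, or about 194 to 196 randomized at 90% evaluable.
- Effect, at 50 per arm: (1.2816 + 1.2816) × 0.36 = 0.92 log10.
- Residual SD, at 50 per arm: 0.7/(2.5632 × 0.2) = 1.37. As a baseline-to-change correlation this is √(1 − (1.366/1.8)²) = 0.65.

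**Effect of the ANCOVA covariate.** With residual SD = 1.8 × √(1 − r²) and 50 per arm, the power is as follows. The values of r are assumptions; the documents give none.

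| r | 0 | 0.3 | 0.5 | 0.6 | 0.65 | 0.7 |
|---|---|---|---|---|---|---|
| Power | 74.6% | 77.5% | 83.2% | 87.5% | 89.9% | 92.5% |

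**Evaluable share.** Section 1.1 reports that of the 70 patients in the Part A interim analysis 62 were evaluable for virology, and of these "58 had baseline quantitative viral load data". Applied to 110 randomized:

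- 62/70 = 89% gives about 97 patients and 73.8% power.
- 58/70 = 83% gives about 91 patients and 71.7% power (71.4% by t). This share is relevant because the ANCOVA needs a quantitative baseline.

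**The case against.** The strongest defence is that 1.8 is the SD of raw change, while the planned analysis is ANCOVA, whose residual SD could be smaller. This is a real second route to 90%, and it means that 75% understates the power of the planned analysis if baseline and change are correlated. It does not rescue the sentence as written: the route needs a correlation of about 0.65, and the protocol gives no correlation and no residual SD. The SAP's own calculation for this endpoint in Part A (Section 7.1: difference 1, SD 2, 90% quantifiable, at least 85% power) needs no covariate gain. Ninety percent of 182 is about 82 per arm; SE = 2 × √(2/82) = 0.312; Φ(1/0.312 − 1.960) = 89%.

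Pooling Part A placebo patients would not help enough either. The synopsis keeps efficacy analyses separate by part unless otherwise indicated, and adding an assumed 36 to 40 controls gives only about 82%.

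The second defence is that little depends on the figure. Part B is descriptive, with no success criterion or futility rule; 95% confidence intervals will show the imprecision; and the Changes to Planned Statistical Analyses Form of 16 March 2022 says the study is ending early and that Part B patients will only be listed. This stands as a limit on the practical harm, and makes over-reading of a formal null result less likely.

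It is also fair that the documents do not say 110 was derived from this calculation. The target of 190 less the 81 already randomized leaves 109, so 110 may simply be the remainder. The error therefore lies in the description of what 110 patients deliver and does not by itself show that Part B was sized wrongly. None of these points makes the stated figure correct.

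**Conclusion.** The power statement is wrong in both places. At its own inputs, with 50 evaluable patients per arm, power for a true 0.7 log10 difference at one timepoint is about 75%, some 15 points below the stated minimum. The type II error is about 25%, two and a half times the implied maximum of 10%. This assumes that 100 is the two-arm total, which the 110 planned subjects and 1:1 allocation establish, and that 1.8 is the SD governing the comparison, which is how the protocol labels it. A lower ANCOVA residual SD would raise the figure, but only a correlation of about 0.65 or more would reach 90%. A lower evaluable share would reduce it to about 72% to 74%.

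The arithmetic is certain; the per-arm/total mix-up is the probable cause only. Because this is the sole power justification given for Part B, it should be corrected even though Part B's analyses are descriptive.

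**What to change.** In Section 8.2.1 and in the Part B paragraph of the synopsis, replace the power sentence with, for example: With 100 evaluable patients (50 per arm), an SD of 1.8 log10 copies/mL for change from baseline and a one-sided 0.1 level test at a single timepoint, power is about 75% to detect a true difference of 0.7 log10 and 90% to detect about 0.92 log10.

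If a gain from baseline adjustment was intended, state the assumed residual SD or correlation and its source, and quote the power that follows from it. Any report that repeats the Part B sample-size rationale should carry the corrected figure.

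The change is wording only. No patients, visits or analyses are added; the cost is a less favourable stated power. If 90% power for 0.7 log10 was truly required, the sponsor should acknowledge that the stated inputs call for 174 to 176 evaluable patients.
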